All participants will complete a BAT with a live tarantula. This phase of the experiment consists of 9 steps, lasting 30 seconds each with a 30 second pause between each step. During the BAT, self-reported and physiological data will be collected at each step. Skin conductance response (SCR) and heart-rate variability (HRV) will be utilized as physiologic measures of fearful arousal using BIOPAC MP150 hardware and AcqKnowledge version 4.2 software (BIOPAC Systems, Inc.).(Appelhans & Luecken, 2006; Choi et al., 2017; Christopoulos, Uy, & Yap, 2016; Laine, Spitler, Mosher, & Gothard, 2009; Thayer, Åhs, Fredrikson, Sollers, & Wager, 2012; Williams et al., 2001) Baseline SCR and HRV will be measured during a 3-minute prior to initiation of a BAT. SCR will be recorded from electrodes attached to the subjects' second and third fingers. Average SCRs and peak SCRs at each step will be measured and compared to individual baselines. HRV will be calculated from R-R intervals in a lead II electrode configuration recording; average HRVs from each step will be compared to individual baselines. The steps are as follows:

- 1. Stand 5 feet away from tarantula in closed terrarium
- 2. Stand 1 foot away from tarantula in terrarium with top removed
- 3. Place both hands on the side of terrarium with top removed
- 4. Touch nose against the glass of terrarium while looking at the tarantula
- 5. Place gloved hand halfway inside terrarium
- 6. Place gloved hand inside terrarium with all fingertips touching base of terrarium
- 7. Place bare hand inside terrarium with all fingertips touching base of terrarium
- 8. Touch the back of the tarantula's leg continuously with a Q-tip
- 9. Touch the back of the tarantula's leg continuously with the tip of the index finger

Prior to beginning the BAT, all participants will be read the following instructions (from BAT Admin Script): "This part of the experiment consists of 9 steps, each lasting 30 seconds. Instructions for each step will be read aloud before you proceed to the next step. Each step

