must be completed before moving on to the next step, and steps much be completed in sequential order. During each step, your heart rate and sweating will be recorded via the electrodes on your chest and finger. After the experimenter reads the instructions for the next step and prior to completing the step, you will also be asked to rate your confidence level to complete the step on a scale from 0 to 100 (0= no confidence, 25= mild confidence, 50= moderate confidence, 75= high confidence, 100 = complete confidence) and your anticipatory distress on a scale from 0 to 100 (0=no distress, 25=mild distress, 50=moderate distress, 75= high distress, 100= severe distress). After completion of each step, you will be asked to rate your maximum level of distress during the step on a scale from 0 to 100. You are entitled to withdraw at any step if you do not wish to continue. Do you have any questions before we begin? The first step of the experiment is to stand 5 feet away from the tarantula while it is in its closed container for 30 seconds. The final step of the experiment is to touch the back of the tarantula's leg with the tip of your index finger continuously for 30 seconds." Before beginning the BAT and after ensuring comprehension of the above instructions, the experimenter will ask the participant to rate his/her overall confidence and overall anticipatory distress with respect to his/her ability to complete all nine steps (see rating scales in above instructions). Before each subsequent step, the participant will be asked to rate his/her confidence and anticipatory distress regarding his/her ability to complete that particular step. During each step, the experimenter will record the spider's movement on a categorical scale (0 = no movement, 1 = a little movement, 2 = a lot of movement). After each step, the participant will be asked to rate his/her maximum level of distress while completing that particular step. Finally, the experimenter will record the number of steps willingly completed for a given participant.

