This visit will occur five to seven days after Day 3. All participants will complete the Spider Phobia Questionnaire (SPQ; Klorman et al, 1974) and Fear of Spiders Questionnaire (FSQ; Szymanski & O'Donohue, 1995), uploaded in Section 10.1, Item 1.0, to test for change in arachnophobia fear/avoidance symptoms as a function of TMS treatment received. Next, all participants will complete an identical BAT to that completed at their first visit with the same tarantula (see DAY 1 above). Self-report and physiological (i.e., SCR) data will again be collected. After completion of these forms, participants will be debriefed by an un-blinded member of the study team and informed to which group they are assigned. They will be

encouraged to discuss whatever questions or concerns they have regarding the study at that time.

After completion of Day 4, participants will be compensated for their time with one credit per hour of study participation.

Dependent variables (DVs) will be quantitative self-reports and behavioral symptoms of fear and avoidance of spiders both pre- and post-treatment, including SCR (difference between baseline and average level during BAT anticipation period, and number of peaks during BAT), total number of steps completed during the BAT, self-reported distress, anticipatory distress, and maximum distress per BAT step, and total score on the SPQ. BAT measures will be collected for each step and therefore minima, maxima, and means will be compared between the two groups. Primary outcomes examined will be number of steps completed during BAT, self-reported distress during BAT, number of SCR peaks during BAT, SPQ score, and FOS score. All other variables examined will be secondary outcomes. Additionally, for feasibility and tolerability assessment, attendance to TMS treatment sessions and early termination of TMS treatment sessions will be recorded. The primary independent variable examined will be the treatment group (iTBS vs. control iTBS). The sample size will be 40 participants (20 per group). Pre-comparison ANOVA will be performed to limit type 1 error due to multiplicity of comparisons.

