Hypotheses will be tested using between-group two-tailed t-tests given that we are testing not only for magnitude of an effect, but also direction of an effect. We expect that comparisons of efficacy will demonstrate increased confidence during BAT approach, decreased endorsed fear of spiders as measured by SPQ and FSQ, and reduced physiologic response to stimulus (reduced HRV and SCR) with active iTBS and exposure when compared to control iTBS and exposure. We expect that comparisons of feasibility and tolerability will show no significant difference between attendance to, early termination of, or subjective tolerability ratings of TMS treatment sessions between treatment groups.

NOTE 2/2/21: the above reported statistical analysis plan was modified given the small sample size, technical limitations, and distributions of the data observed. The number of statistical tests performed was minimized and multi-level mixed-effects models (MLMs) and nonparametric tests were utilized as appropriate based on the sample size of the experiment. Behavioral measures acquired during the BATs (anticipatory distress, maximum distress, mean skin conductance at each step) were examined using MLMs in Stata version 16.1 as functions of BAT step, group assignment, and timepoint (pre or post-treatment). All other analyses were performed in SPSS (version 26.0.0.0). Demographics and experimental parameters were analyzed for between-group differences using 2-sided Mann-Whitney U Tests. Changes in self-reported fear of spiders (SPQ and FOS) were analyzed using a repeated-measures MANOVA (Greenhouse Geisser correction was applied in case of non-sphericity). A pair of chi-square analyses were performed to validate blinding of the study (based on questionnaires completed by subjects and raters), and no significant deviation from 50/50 chance was observed. A p-value of <0.05 was considered significant for all testing.

ADVERSE EVENT MANAGEMENT

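### The primary SCR peak count has no fixed summary although participants decide how many BAT steps are recorded, and the 2/2/21 note does not say what became of it

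*Combined protocol and SAP*

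**What the plan says.** **The test.** DAY 1 describes the BAT: "This phase of the experiment consists of 9 steps, lasting 30 seconds each with a 30 second pause between each step". Steps are taken in order, and the script read to participants says: "You are entitled to withdraw at any step if you do not wish to continue". The experimenter records how many steps were willingly completed.

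**The outcomes.** DAY 4 defines the SCR variables as "difference between baseline and average level during BAT anticipation period, and number of peaks during BAT". The primary list begins: "Primary outcomes examined will be number of steps completed during BAT, self-reported distress during BAT, number of SCR peaks during BAT". The SPQ and the fear-of-spiders score complete the five, followed by: "All other variables examined will be secondary outcomes".

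**The summaries.** Just before that list, DAY 4 says: "BAT measures will be collected for each step and therefore minima, maxima, and means will be compared between the two groups". It does not tie any of the three to the peak count or say which is primary. DAY 1 names the per-step SCR measures: "Average SCRs and peak SCRs at each step will be measured and compared to individual baselines". A count of peaks is not among them.

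**The hypothesis.** The paragraph after DAY 4 expects "reduced physiologic response to stimulus (reduced HRV and SCR) with active iTBS and exposure" relative to control.

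**The 2/2/21 note.** It says the analysis plan was changed and the number of tests kept small. Anticipatory distress, maximum distress and mean skin conductance at each step went into mixed models with BAT step, group and timepoint. Other analyses were run in SPSS. Neither the SCR peak count nor steps completed is named.

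**The concern.** The participant sets the length of the recording, and that length is itself a primary outcome. A total peak count therefore mixes two things: how often arousal responses occur, and how long the person stayed in the test. If active treatment helps people go further, the total can hide a real fall in peak rate, or show a rise that reflects only longer recording.

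The other summaries do not fully escape this. Adding steps can only raise or leave unchanged a maximum over completed steps, and can only lower or leave unchanged a minimum. A mean removes the recording-time effect but still averages over different steps for those who go further.

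This is one of five primary outcomes in a pilot, but it is the only physiological one. Because the note is silent, a reader cannot tell how, or whether, it was tested.

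**Working it through.** The plan gives no expected peak count, peak rate or step count, so there is no figure of its own to reproduce.

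**1. Recording time.** Inputs from DAY 1: 30 s per step, 30 s pauses, at most nine steps. For s completed steps, step time is 30s seconds; with the pauses between steps it is 30(2s − 1). One step gives 30 s. Nine steps give 270 s, or 510 s with pauses.

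**2. Effect on a total.** At an equal peak rate, the excess in the active arm is (active time ÷ control time) − 1. The true rate fall that would be exactly cancelled is 1 − (control time ÷ active time). The step counts below are assumed.

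| Active vs control steps | Excess, step time | Fall cancelled | Excess, with pauses | Fall cancelled |
|---|---|---|---|---|
| 6 vs 6 | 0% | 0% | 0% | 0% |
| 7 vs 6 | 210/180 − 1 = 17% | 14% | 390/330 − 1 = 18% | 15% |
| 8 vs 6 | 240/180 − 1 = 33% | 25% | 450/330 − 1 = 36% | 27% |
| 9 vs 6 | 270/180 − 1 = 50% | 33% | 510/330 − 1 = 55% | 35% |

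**3. Effect on a mean per completed step.** If the peak rate is the same at every step, the mean is unaffected. Suppose instead that the log rate rises by 0.10 per step (assumed), with step 5 set to 1. The relative rates over steps 1–6 sum to 5.240, mean 0.873. Over steps 1–8 they sum to 7.811, mean 0.976. The ratio of means is 0.976/0.873 = 1.12, so 12% higher with no true difference. The ratio of totals is 7.811/5.240 = 1.49.

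**4. Illustration only.** Apart from 20 per arm, the nine-step limit and the two-sided 5% test, every input here is assumed. Steps: mean 5 before treatment, 6 after in control, and +0, +0.5, +1 or +2 in active; person SD 1.5, residual SD 1; limited to 1–9. Peaks: Poisson, 3 per step; person CV 0.5, person-by-visit CV 0.3; correlation −0.5 between a person's rate and steps. Rate flat, or rising as in item 3.

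- No true difference, flat rate, t-test on change in total peaks: the active arm is significantly higher in 31% of trials at 7.7 vs 6.0 mean steps, 12% at 6.9, 6% at 6.4 and 2.4% at equal steps (nominal 2.5%). A Mann-Whitney test gives 31%, 11%, 6% and 2.4%.
- Same comparison using mean peaks per step, at 7.7 vs 6.0: 2.4% (flat), 7% (rising).
- True 25% fall at 7.7 vs 6.0, flat rate: detected in 3% of trials by totals, 26% by mean per step and 38% by a step-level mixed count model. Rising rate: 1%, 15% and 34%.
- The mixed model's two-sided false-positive rate is 5.3% (flat) and 6.9% (rising), so slightly liberal.

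**The case against.** The strongest reply is that the plan does provide a per-step summary. The sentence on minima, maxima and means stands directly before the primary list, and the wording does not favour a total: DAY 4 uses the word total for steps and for the SPQ, but not for peaks. This stands, and it is why one cannot say that the outcome has no denominator. What remains is that three summaries are offered and none is chosen for this outcome.

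Second, the note replaced the t-test plan, and its skin-conductance model already has the step-level structure. A reader might infer that total peaks were compared and gave a biased result. The documents report no such comparison. A reader might also infer that the peak count was dropped because of its result. The documents do not support that either: the note gives general reasons, ties none to this outcome, and is equally silent on steps completed.

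Third, the hypotheses do not predict more steps with active iTBS, and with equal steps there is no bias. That stands. The larger simulated figures also need a large step effect, about d = 1.2 at 7.7 vs 6.0. In that scenario steps completed would itself be significant in 96% of trials, so a careful reader would see the likely cause.

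Finally, this is a pilot, and a total would work against a claim of benefit rather than create one. That limits the stakes but does not settle what the outcome means.

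**Conclusion.** The point holds in a conditional form. A named primary outcome has no fixed summary, and each summary the text permits can depend on how far the participant went, which is another primary outcome. A total is most exposed, rising in proportion to steps at a constant rate. A mean per completed step is least exposed, and is unaffected if the rate does not vary by step.

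The timing arithmetic rests on the protocol; the step counts put into it do not. The actual bias is unknown, is zero if the arms complete the same steps, and could be small. The simulated percentages show the mechanism under one assumed set of inputs and do not estimate what happened in this trial.

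Separately, the note leaves the fate of the peak count unstated. Mean skin conductance is outside the primary list, so under DAY 4's own rule it ranks as secondary unless the sponsor declares otherwise.

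**What to change.** - Define an SCR peak and its counting window (step only, or step plus pause).
- Do not compare total peaks, or minima or maxima taken over unequal numbers of steps.
- Analyse peaks per completed 30-second step in a mixed model suited to counts, with BAT step, group, timepoint and group-by-timepoint, in line with the note's models for the other BAT measures. A Poisson or negative-binomial model with participant and participant-by-visit random effects is one reasonable choice, not the only one.
- Mean peaks per completed step is an acceptable simpler fallback, with the caveat that it still mixes different steps.
- Keep steps completed as its own outcome and report it beside the peak result.
- If the peak count was dropped, or replaced by mean skin conductance, say so, give the reason, and state whether the replacement is primary or secondary.

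The cost is a few lines of text and a little more analysis. SCR is already recorded at each step, so no new data are needed. The change does not cure low power: with 20 per arm, even the step-level model will often miss a moderate fall in peak rate.

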COVER PAGE

Study protocol as of 8/7/19, last reviewed/approved 4/1/2020, current as of 2/2/21 NCT04019054

Transcranial Magnetic Stimulation (TMS) in Conjunction with Exposure Therapy for the Treatment of Spider Phobia

Project Summary:

Spider phobia is an exceedingly common phobia throughout the world. The current standard treatment involves exposure therapy, which consists of a series of brief exposures of an individual to the thing they fear, in this case spiders. This study aims to examine the use of a neuromodulatory technology, transcranial magnetic stimulation (TMS), as a possible treatment option for spider phobia. TMS uses low-intensity electromagnetic energy to stimulate the brain, introducing energy into critical hubs of brain networks to "reset" their function and alleviate symptoms with very few side-effects.

This study will consist of four separate visits. After screening subjects for spider phobia, baseline testing of subjective distress measures and physiologic stress data (heart rate variability and sweat response) during a prolonged spider exposure test will be collected. Subjects will then be placed into one of two groups: one receiving exposure therapy and intermittent Theta Burst Stimulation (iTBS) TMS (active study group), and another receiving exposure therapy with iTBS to a circuit not involved in a phobic reaction (control study group). Subjects will undergo their first treatment session during the first visit following the baseline data collection; the second and third treatments will occur the following two days. The fourth visit will occur one week after the third and consist of the same testing as the first visit; the same data will be collected. Changes from pre- to post-treatment in both subjective and physiologic data will be compared between the treatment and sham groups to examine effects of TMS on spider phobia.

Background and significance

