The experiment will consist of four days. Day 1 will include informed consent, questionnaires, a behavioral approach test with a spider, a series of short exposures with a spider, and the first TMS treatment (for a total of approximately 75-90 minutes). Day 2 will occur one to two days after Day 1 and will consist of a second series of short exposures with a spider and the second TMS treatment (30 minutes). Day 3 will occur one to two days after Day 2 and will also consist of a series of short exposures and a TMS treatment (30 minutes). Day 4 will occur five to seven days after Day 3 and will consist of post-study questionnaires and an identical behavioral approach test as is conducted on the first visit (30 minutes). Participants will be randomized to either an active TMS treatment group (using an iTBS stimulation protocol over the participant's ventro-medial prefrontal cortex, an area involved in phobic response) or a control TMS treatment group (using the same iTBS stimulation protocol over the central sulcus and between hemispheres, a site not associated with memory or fear response).

Prospective participants will be undergraduate students recruited through the UCLA Psychology Department Subject Pool (i.e., SONA). At this time, this small pilot study is not equipped to recruit from the population at-large, and therefore is currently limited to recruitment through SONA. All prospective participants will be screened with the 31-question Spider Phobia Questionnaire (SPQ) to ensure eligibility for participation, with a minimum total score equal to or greater than 17 required for participation.(Klorman, Weerts, Hastings, Melamed, & Lang, 1974) Participants will be enrolled for the study only if they are able to complete all four visits of the experiment. Exclusion criteria will include:

1) Subject is mentally or legally incapacitated, unable to give informed consent.

- 2) Subjects with psychosis (psychotic depression, schizophrenia, or schizoaffective diagnoses (lifetime)); bipolar disorder (lifetime); dementia (lifetime); delirium within the past 6 months; eating disorder within the past year; obsessive-compulsive disorder (lifetime); post-traumatic stress disorder within the past year; acute risk for suicide or self-injurious behavior. Patients with diagnostic uncertainty or ambiguity (e.g. rule-out pseudodementia of depression) will be excluded.

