Next, all participants will engage in a series of exposure practices with a different live tarantula from the one they saw during the BAT. Exposure therapy will consist of a series of 10 identical exposure trials of a 30-second duration with a 30-second pause between trials. Participants will be asked to place an ungloved hand in the terrarium (with all fingertips touching the base of the terrarium) on the opposite end of the terrarium as the tarantula during the trial. Prior to completing the series of exposures, participants will be asked about their feared outcome concerning approaching the tarantula (e.g., being bitten). Participants are entitled to withdraw at any step during exposures and will not be prevented from further continuation in the study.

Following the series of exposures, participants will undergo TMS treatments using an iTBS protocol. Before the first iTBS treatment, the TMS coil will be calibrated to the subject's individual resting motor threshold (RMT), or the minimum stimulus intensity necessary to elicit a motor response in the right abductor pollicis brevis (APB) or first dorsal interosseus (FDI) muscles for ≥ 50% of stimuli applied to the motor cortex. After initial calibration, the TMS coil will be placed over the subject's ventral medial prefrontal cortex (vmPFC; as determined using position Fpz of the international 10-20 EEG electrode system), a TMS target shown to affect phobic response.(Baeken et al., 2010; Guhn et al., 2012, 2014; Suarez-Jimenez et al., 2018) Stimulation intensity of 100% of the individual RMT in bursts of three pulses at a frequency of 50 Hz every 200 ms on top of a 5Hz carrier wave. Pulse delivery is over 2 s and repeated every 10 s, 20 times in succession, for a total of 600 pulses delivered in 3.33 minutes.(Baeken et al., 2010; Bulteau et al.,

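### The primary BAT step count is capped at 9 with no BAT entry limit, so Day 1 completers cannot improve, and no analysis that allows for this is named

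*Combined protocol and SAP*

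**What the plan says.** All references are to the combined protocol and SAP.

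- **Outcome (DAY 4).** "Primary outcomes examined will be number of steps completed during BAT". Four more follow in the same sentence: distress ratings, SCR peaks, and the SPQ and FOS totals. Steps completed is thus one of five primary outcomes.
- **Scale (DAY 1).** "This phase of the experiment consists of 9 steps, lasting 30 seconds each with a 30 second pause between each step". Steps are taken in order, and the score is the count the participant was willing to complete. The last step is "Touch the back of the tarantula's leg continuously with the tip of the index finger"; nothing lies above it.
- **Entry (OVERVIEW).** Severity is judged on the SPQ alone, "with a minimum total score equal to or greater than 17 required for participation". The Day 1 eligibility check comes before the BAT and contains no BAT item.
- **Repeat test (DAY 4).** The same BAT, with the same tarantula.
- **Exposure, both arms (DAY 1 to DAY 3).** Ten trials at each of three visits. "Participants will be asked to place an ungloved hand in the terrarium (with all fingertips touching the base of the terrarium"), at the end away from the tarantula. BAT step 7 reads "Place bare hand inside terrarium with all fingertips touching base of terrarium".
- **Analysis.** The Project Summary says "Changes from pre- to post-treatment in both subjective and physiologic data will be compared between the treatment and sham groups". The paragraph after the outcome list plans two-tailed between-group t-tests, preceded by an ANOVA meant to limit type 1 error. The 2/2/21 note then replaces this with mixed models for anticipatory distress, maximum distress and mean skin conductance, a repeated-measures MANOVA for SPQ and FOS, and nonparametric tests where suitable. It does not say how steps completed was analysed.

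**The concern.** A participant who scores 9 on Day 1 can have a change of at most 9 - 9 = 0, whatever the treatment does. One who scores 7 can gain at most 2. Nothing in the entry criteria keeps such people out, and no rule says how they are handled. Both arms also receive exposure therapy, so controls may move up the same short scale. If many participants are near the top, a true advantage of active iTBS is recorded as smaller than it is, and a t-test on change loses power on the only primary outcome that measures avoidance by behaviour.

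**Working it through.** **1. The plan's own figure.** The sample size is 40 (20 per group). No effect size, SD, power or expected step score accompanies it, so it cannot be reproduced. At a two-sided 0.05, 20 per arm gives 80% power for a standardised difference of 0.909 by t-test (0.886 by normal approximation).

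**2. What is certain.** Maximum score 9, identical test on Day 4, no BAT criterion. The gain for a Day 1 completer is at most 0.

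**3. How many completers.** The share is not given. If it is 5%, 40 × 0.05 = 2 are expected, and the chance of at least one is 1 - 0.95^40 = 0.87. At 10% the figures are 4 and 0.985; at 20%, 8 and above 0.999.

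**4. Effect on power.** These inputs are assumptions; none is in the documents:
- 20 per arm, latent approach score with SD 2.5 steps, Day 1 to Day 4 correlation 0.6
- gain of 2 steps in both arms, plus a true active advantage of 2 steps
- recorded score = latent score rounded down and limited to 0-9

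Without a cap, the SD of change is 2.5 × √(2 × (1 - 0.6)) = 2.236. The standardised difference is 2/2.236 = 0.894, and power is about 79%.

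With the cap, the share at 9 is 1 - Φ((9 - mean)/2.5). For a Day 1 mean of 5:
- Day 1: 1 - Φ(1.6) = 5%
- Day 4 controls (mean 7): 1 - Φ(0.8) = 21%
- Day 4 active (mean 9): 1 - Φ(0) = 50%

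Simulated power:

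| Day 1 mean | t-test on change | Rank ANCOVA, Day 4 on Day 1 steps |
|---|---|---|
| 2 | 80% | 81% |
| 5 | 57% | 79% |
| 6 | 42% | 72% |
| 7 | 26-28% | 60-63% |

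The 80% at a mean of 2 is within simulation error of the uncapped 79%. At means of 3 and 4 the t-test has 76% and 68%. The recorded difference falls from 2.0 steps to 1.45, 1.16 and 0.84 at means of 5, 6 and 7. With no true difference, rejection was near 5%.

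**5. Sensitivity.** Rounding to the nearest step instead of down gives 49%, 34% and 21% for the t-test at means of 5, 6 and 7, and 74%, 67% and 57% for rank ANCOVA. Also with rounding, and a true advantage of 2.03 steps (80% power uncapped), gains of 1, 2 or 3 steps in both arms give the t-test 75-80% at a mean of 2; 65%, 51% and 32% at 5; and 39%, 21% and 10% at 7.

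**6. Where the recovery comes from.** Ordinary ANCOVA on raw steps gives 78%, 72% and 60% at means of 5, 6 and 7. Most of the gain is therefore adjustment for baseline in place of a change score. The matching uncapped benchmark for ANCOVA is about 86%, so the cap still costs power.

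**The case against.** - **The t-test plan has been superseded.** This stands in part. The 2/2/21 note withdraws it and mentions nonparametric tests, one of which may have been used for steps. But the note assigns no method to this outcome, so the t-test is still the only one stated.
- **Change may not be the planned contrast.** Fair. The Project Summary sentence on change covers subjective and physiologic data, while steps are behavioural. DAY 4 says only that dependent variables are measured before and after treatment. A t-test on Day 4 scores alone would lose less: 55-66% against about 70% uncapped at a Day 1 mean of 5, with rounding and an advantage of 2.03 steps.
- **A low start is possible.** Entrants have an SPQ of 17 or more, and steps 8 and 9 require touching the tarantula. With a Day 1 mean of 2 or 3 little is lost.
- **Exposure is not simply step 7.** The hand position matches, but exposure puts the hand at the far end and uses a different tarantula. Participants may also withdraw from trials, so 30 is a maximum.
- **Other primaries cover it.** Distress and SCR peaks are still recorded in people who finish all 9 steps. But a step's maximum distress is rated only after that step is completed, so it depends on how far the person got and does not replace the count.
- **It is a small pilot.** True, and this limits the weight of any one test. It does not remove the need to say how a primary outcome is analysed.

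**Conclusion.** The point holds as a structural limit with a possible, unmeasured cost. The cap, the absence of a BAT entry criterion, the unchanged Day 4 test and the zero maximum gain for Day 1 completers follow directly from the text. The loss of power does not: it runs from almost nothing at a Day 1 mean of 2 to about two thirds of the uncapped power at a mean of 7 (79% down to 26-28%), and every figure in that range rests on assumed inputs.

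A reader might infer that the arms do pile up at 9 by Day 4. The documents do not support this. They give no step distribution, and the note, although it cites the observed data distributions as a reason for change, mentions no ceiling. Nor does the 70-75% benefit of exposure therapy in the Background show it: that is a cited figure against placebo, not a forecast for this trial or a rate of completing step 9.

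The change is worth making because the alternative analysis did as well as or better than the t-test on change at each Day 1 mean compared, including the low one.

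**What to change.** 1. Name the analysis of steps completed: Day 4 steps as an ordered outcome adjusted for Day 1 steps, by rank ANCOVA or a proportional-odds model, in place of a t-test on change. Keep everyone in by assigned group, including Day 1 completers.
2. Report the number at step 9 and the plain step counts by arm and visit, so that readers can see whether a ceiling occurred.
3. Label the analysis post hoc, and state which test was actually used for steps when the plan was revised.
4. Breaking ties at 9 by the step-9 distress rating should be at most a sensitivity analysis. At Day 1 means of 5, 6 and 7 it gave 80%, 78% and 75% power when distress was simulated to follow the latent approach score, but 75%, 63% and 46% when it was unrelated, against 78%, 72% and 62% with no tie-break. Distress is also already a separate primary outcome.

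**Cost.** No new data are needed; the work is analysis wording and one table. A rank or odds-ratio result is less direct to read than a mean change in steps, which the plain counts offset. It is also a further choice made after data were seen, so it cannot carry the weight of a prespecified test.
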